### 10.3 Analysis Populations

The following analysis populations will be used for presentation of the data:

- **Intent-to-treat (ITT) Population:** The ITT population includes all randomized patients, independent of whether they received the study medication or not. All primary efficacy analyses will be based on the ITT population. All patients in the ITT population will be analyzed according to the treatment they were randomized to receive and not according to what they actually received, if different.
- **Per-Protocol (PP) Population:** The PP population includes all patients in the ITT population who have no major violations of the inclusion/exclusion criteria. Patients in this population will be analyzed according to the treatment to which they are randomized. The analyses using data from the PP population are considered supportive and sensitivity analyses.
- **Response-Evaluable (RE) Population:** The response-evaluable population is defined as all patients in the ITT population who received at least 1 dose of avapritinib or regorafenib, have at least 1 target lesion per mRECIST, version 1.1, at Baseline and have at least 1 postbaseline disease assessment by central radiology per mRECIST, version 1.1. Selected efficacy analysis may be performed using the RE population.
- **Safety Population:** The safety population is defined as all patients who received at least 1 dose of study medication. The safety population will be analyzed according to the treatment the patient actually received.
- **PK Population:** The PK population is defined as all patients who have adequate PK samples collected so that the PK parameters can be assessed and calculated.

## 10.4 Randomization and Stratification

Eligible patients will be randomized in a 1:1 ratio to receive avapritinib or regorafenib, stratified by line of therapy (third vs. fourth), geographic region (Asia vs. rest of the world), and mutation status measured in ctDNA or a tumor sample (PDGFR $\alpha$  D842V mutation present vs. absent). The randomization scheme will be generated by an independent statistical group. The randomization assignment will be implemented by an IWRS.

## 10.5 Statistical Methods

### 10.5.1 Disposition

A tabulation of the disposition of patients will be presented by treatment arm, including the number of patients randomized, patient distribution for each stratification factor, the number treated, the reasons for treatment discontinuation, and the reasons for study discontinuation. Entry criteria and protocol deviations will be listed.

### 10.5.2 Demographic and Baseline Characteristics

Demographic and baseline disease characteristic data will be presented by treatment arm. Data to be tabulated will include sex, age, and race and ethnicity, as well as disease-specific information.

### 10.5.3 Efficacy Analysis

#### 10.5.3.1 Analysis of the Primary Efficacy Endpoint

The primary endpoint of PFS is defined as the time from randomization to disease progression or death due to any cause, whichever occurs first. The primary analysis for PFS is based on the central radiological assessment of PD per mRECIST, version 1.1 in the ITT population.

Patients without disease progression or death at the time of analysis will be censored at their last date of tumor evaluation. Patients who withdraw from the study and receive subsequent antineoplastic therapy without documented PD will be censored at the time of the last adequate (CT or MRI scan available) disease assessment. For PD documented between scheduled evaluations, the actual date of PD will be used, not the date of the next scheduled evaluation. For death or PD after no more than 1 missed evaluation, the date of the event will be the date of PD or death, whichever occurs first. For death or PD after more than 1 missed evaluation, the date of the event will be censored at the last adequate disease assessment. Detailed censoring methods will be described in the statistical analysis plan (SAP).

The Kaplan-Meier method will be used to estimate the distribution of PFS for each treatment group. The primary treatment comparison is based on a stratified log-rank test in the ITT population. The HR, and its 95% CI, are to be estimated based on a stratified Cox's model with treatment as the explanatory variable. Stratification factors include TKI

treatment (third vs. fourth), geographic region (Asia vs. rest of the world), and mutation status measured in ctDNA or a tumor sample (PDGFR $\alpha$  D842V mutation present vs. absent).

Progression-free survival derived from the Investigator assessment per mRECIST, version 1.1 in the ITT population, and from central radiological assessment per Choi criteria in the ITT population will be evaluated and used as supportive evidence. The analysis of PFS based on the PP population will also be included as a sensitivity analysis.

### 10.5.3.2 Analyses of Secondary Efficacy Endpoints

#### 10.5.3.2.1 Objective Response Rate

Objective response rate is defined as the percentage of patients whose best response is CR or PR as assessed by central radiological assessment according to mRECIST, version 1.1. The ORR will be evaluated and analyzed for the ITT population.

Objective response rate will be summarized for each treatment group. A stratified Cochran-Mantel-Haenszel (CMH) test will be performed to test treatment difference. A logistic regression model will be used to estimate the treatment effect measured in terms of odds ratios. The odds ratio and its 95% CI will be presented.

A gate-keeping method will be implemented to control Type I error. The ORR will be analyzed when superiority is demonstrated for PFS.

Additionally, response as assessed by investigator per mRECIST, version 1.1 and response based on central radiology per Choi criteria will be evaluated and analyzed for the ITT population as supportive analysis. All the proposed response assessments will be examined based on the response-evaluable population and/or per protocol population, as sensitivity analyses.

#### 10.5.3.2.2 Overall Survival

Overall survival is defined as the time from date of randomization to death due to any cause. The primary treatment comparison will be based on a rank preserving structural failure time (RPSFT) model to account for treatment crossover effects from regorafenib to avapritinib. The survival time gained/lost by receiving avapritinib after crossover in the regorafenib group will be estimated. Rank preserving structural failure time reconstructs the survival duration of patients as if they had never received avapritinib, assuming treatment is acting by multiplying survival time by a given factor once a patient starts receiving avapritinib ([Korhonen et al, 2012](#)).

If the patient is alive or the vital status is unknown at the time of analysis, OS will be censored at the date the patient is last known to be alive. The Kaplan-Meier method will be used to estimate the distribution of OS for each treatment group. The HR and its 95% CI will be estimated based on Cox's regression model with stratification factors as covariates.

In addition, the probability of survival by time after randomization based on Kaplan-Meier estimates will be tabulated for each treatment group along with the standard errors estimated by the Greenwood formula.

A gate-keeping method will be implemented to control Type I error. The OS will be analyzed when superiority is demonstrated for both PFS and ORR. The OS will also be analyzed at the follow-up when 264 events (deaths) occur.

A sensitivity analysis will be conducted in the ITT population where treatment crossover is ignored. Other sensitivity analyses may be considered as appropriate.

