The key secondary endpoints are: ORR and OS. The ORR, as assessed by central radiological assessment according to mRECIST, version 1.1, will be evaluated and analyzed for the intent-to-treat population. A stratified Cochran-Mantel-Haenszel test will be performed to test treatment difference. A logistic regression model will be used to estimate the treatment effect measured in terms of odds ratios.

The primary treatment comparison for OS will be based on a rank preserving structural failure time model to account for treatment crossover effects from regorafenib to avapritinib. The survival time gained/lost by receiving avapritinib after crossover in the regorafenib group will be estimated. Rank preserving structural failure time reconstructs the survival duration of patients as if they had never received avapritinib, assuming treatment is acting by multiplying survival time by a given factor once a patient starts receiving avapritinib (Korhonen et al, 2012). If the patient is alive or the vital status is unknown at the time of analysis, OS will be censored at the date the patient is last known to be alive. The Kaplan-Meier method will be used to estimate the distribution of OS for each treatment group. The hazard ratio and its 95% confidence interval will be estimated based on Cox's regression model with stratification factors as covariates.

A gate-keeping method will be implemented to control Type I error. The ORR will be analyzed when superiority is demonstrated for PFS. The OS will be analyzed when superiority is demonstrated for both PFS and ORR.

Safety will be evaluated by the incidence of AEs, causality, intensity, seriousness, and type of AEs, and by the patient's vital signs, ECOG PS scores, clinical laboratory test results, and ECG data. All safety data will be listed by patient and summarized by treatment arm.

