**Avapritinib**  
**Statistical Analysis Plan Study BLU-285-1303**

**1. INTRODUCTION**

This statistical analysis plan (SAP) describes the statistical analyses and data presentations to be performed for Blueprint Medicines, Protocol No. BLU-285-1303 (amendment 3 dated 20 JUN 2019) ‘An International, Multicenter, Open-label, Randomized, Phase 3 Study of Avapritinib (BLU-285) vs Regorafenib in Patients with Locally Advanced Unresectable or Metastatic Gastrointestinal Stromal Tumor (GIST)’. It contains definitions of analysis populations, derived variables, and statistical methods for the analysis of efficacy and safety. It is to ensure that the data listings, summary tables, and figures which will be produced, and the statistical methodologies that will be used, are complete and appropriate to allow valid conclusions regarding the study objectives.

The SAP will be finalized and approved prior to the clinical database lock for the final analysis, when approximately 264 progression free survival (PFS) events are reached. The analyses of safety, efficacy and pharmacokinetics will include all data collected in the database through the data cutoff date.

A follow-up analysis for overall survival will be conducted when approximately 264 deaths have been observed. Additional data collected after the database lock from the primary analysis of the study will be prepared as an addendum to the study report per regulatory or scientific need.

Selected analyses from this SAP will be performed for the Independent Data Monitoring Committee (IDMC) to review accumulated data from the study. Further details are described separately in the IDMC Charter.

Analysis of pharmacokinetics (PK) is outside the scope of this SAP and will be addressed separately.

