#### *4.6.3.2 Overall Survival*

Overall survival is defined as the time from randomization to the date of death. Patients who die before or on the data cutoff date will be considered to have had an OS event. All patients who do not have a death record prior to or on the cutoff date will be censored at the last date known alive.

The primary treatment comparison will be based on a stratified log-rank test using the ITT Population. The HR and its 95% CI will be estimated using a stratified Cox model with treatment as the explanatory variable and strata as the stratification factors. An unstratified log-rank test will be performed as a sensitivity analysis.

A rank preserving structural failure time (RPSFT) model will be applied as a supportive analysis to account for treatment crossover effects from regorafenib to avapritinib. The survival time gained/lost by receiving avapritinib after crossover in the regorafenib group will be estimated. The RPSFT reconstructs the survival duration of crossover patients as if they had never received avapritinib, assuming treatment acts by multiplying survival time by a given factor once a patient starts receiving avapritinib (Korhonen et al, 2012). See Appendix 2 (Section 7.4) for further details of implementing this method.

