**6. CHANGES TO PLANNED ANALYSES FROM THE PROTOCOL**

There is no change to planned analyses from the protocol.

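### For OS, the SAP reverses the protocol's primary and sensitivity analyses while declaring no change, and neither document says whether the HR of 0.67 behind 264 deaths allows for crossover

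*Protocol*

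**What the plan says.** **Protocol.** Section 10.5.3.2.2 states: "The primary treatment comparison will be based on a rank preserving structural failure time (RPSFT) model to account for treatment crossover effects". The Study Summary (Statistical Methods and Data Analysis) repeats it: "The primary treatment comparison for OS will be based on a rank preserving structural failure time model". For the unadjusted analysis, Section 10.5.3.2.2 adds: "A sensitivity analysis will be conducted in the ITT population where treatment crossover is ignored". The OS HR is to come from a Cox model with the stratification factors as covariates. OS is analysed once PFS and ORR have both succeeded and again at 264 deaths, with no rule for dividing alpha between the two looks.

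**SAP.** The introduction ties the SAP to protocol amendment 3 of 20 June 2019. Section 4.6.3.2 states: "The primary treatment comparison will be based on a stratified log-rank test using the ITT Population". The RPSFT "model will be applied as a supportive analysis to account for treatment crossover effects from regorafenib to avapritinib". The Cox model is stratified. Sections 4.6.1 and 5 add a formal OS interim with O'Brien-Fleming-type Lan-DeMets spending. Section 6, which exists to declare departures, reads in full: "There is no change to planned analyses from the protocol".

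**Sample size.** Protocol 10.2 and SAP 1.3 carry the PFS effect (HR 0.67) and the 264 events over to OS. Neither mentions crossover there, although Protocol 7.6 lets regorafenib patients move to avapritinib after centrally confirmed progression, and SAP 7.4 says that crossover can make the conventional analysis understate the effect.

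**The concern.** Protocol 2.2 and 10.2 and SAP 4.6.1 place OS third in a fixed testing sequence, so its primary analysis carries a confirmatory claim. Two current documents name different analyses for that role, neither says which document prevails, and the section that should disclose the change denies it. A later reader of the study report could fairly ask which analysis was prespecified and when the choice was made.

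Two things are at stake. One is error control: an RPSFT analysis can be tested in more than one way, and not every way keeps the 5% level. The other is the OS power claim: 264 deaths is right only for the HR of the comparison actually tested, and crossover pulls the ITT HR towards 1.

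**Working it through.** **Step 1. The two texts side by side**

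| Item | Protocol 10.5.3.2.2 | SAP | Listed in SAP Section 6? |
|---|---|---|---|
| Primary OS comparison | RPSFT | Stratified ITT log-rank (4.6.3.2) | No |
| Other analysis | ITT ignoring crossover, as sensitivity | RPSFT, as supportive (4.6.3.2) | No |
| Cox model for the HR | Stratification factors as covariates | Stratified (4.6.3.2) | No |
| Alpha for two OS looks | Not specified | Lan-DeMets spending (4.6.1, 5) | No |

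The first two rows are a reversal. The third changes estimation only. The fourth fills a gap in the protocol and is an improvement, but it is still an undeclared addition.

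**Step 2. Does the reversal change the p-value?**

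SAP 7.4 defines the adjusted time as U = T_off + T_on × exp(psi) and finds psi by setting a log-rank statistic by randomized arm to zero.

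- At psi = 0, exp(psi) = 1 and U = T_off + T_on = T, the observed time. The g-estimation test of psi = 0 is therefore the log-rank test on the observed times by randomized arm, which is the ITT test. The p-values coincide if both tests use the same stratification. SAP 4.6.3.2 stratifies its ITT test; SAP 7.4 does not mention stratification.
- SAP 7.4 does not say that this is the test. After transforming the switchers' times, it leaves the analysis to an unspecified suitable method. An ordinary log-rank test at that stage treats the estimated psi as known. If the observed difference favours avapritinib, exp(psi) falls below 1, the switchers' times shrink, and the arms move further apart than they did in the ITT data.
- Illustration under the null. Assumed: control OS median 12 months (Protocol 1.4 says about 1 year), control PFS median 5 months (Protocol 10.2), 50–70% of control progressors switching, progression independent of death, uniform 18-month accrual, cutoff at 264 deaths, unstratified, single look, 1,500 simulated trials per scenario. The test on transformed times rejected in 9–14% of trials at a nominal two-sided 5%, with or without re-censoring. The ITT test rejected in 5–6%.

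**Step 3. Reproducing 264**

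Inputs from Protocol 10.2 and SAP 1.3: HR 0.67, 90% power, two-sided alpha 0.05, 1:1 allocation.

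- Deaths = 4 × (1.960 + 1.282)² / (ln HR)². With ln 0.67 = −0.4005, this is 42.03 / 0.1604 = 262.1, so 263 (Schoenfeld). Freedman's formula gives 270. The planned 264 reproduces.
- Power = Φ(√264 / 2 × |ln HR| − 1.960) = Φ(8.124 × 0.4005 − 1.960) = Φ(1.294) = 90.2%.

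**Step 4. The same formulas at other ITT HRs**

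| HR in the tested (ITT) comparison | Power at 264 deaths | Deaths for 90% power |
|---|---|---|
| 0.67 | 90% | 263 |
| 0.70 | 83% | 331 |
| 0.75 | 65% | 508 |
| 0.80 | 44% | 845 |

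From 0.75 upward, the deaths needed exceed the 460 patients planned. This table needs no crossover assumption.

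To show how such HRs could arise, take a no-crossover HR of 0.67, a control OS median of 12 months and a control PFS median of 5 months, and let 70% of control patients alive at the switch point (half a month after progression) cross over. If their later hazard is multiplied by 0.67, the average ITT HR is about 0.75 and power 64%. If it is multiplied by 0.80, they are about 0.71 and 79%. The switching share and post-switch effect are assumed; the documents give neither.

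**The case against.** **The SAP governs and is clear.** It names one OS test, gives its spending rule and fixes the timing: "The SAP will be finalized and approved prior to the clinical database lock for the final analysis". This stands. A reader might infer that the choice of OS analysis stays open until after unblinding; the documents do not support that. What remains is that the SAP departs from the protocol it cites and says that it does not.

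**The two analyses may give the same p-value.** A reader might infer that the reversal must change whether OS is significant. It need not: with the test of psi = 0 and matching stratification, only the HR and CI differ. This limits the consequence but does not remove it, because neither document specifies that test.

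**The OS power claim is sound as it reads.** In the SAP the OS analysis is the ITT log-rank test, so 0.67 can be read as the HR of that comparison. The arithmetic is right on that reading, and naming one test in both documents would narrow the ambiguity. This is why the power point is secondary. A reader might infer that 264 is an error or that OS is underpowered by a known amount. The documents support neither, since they give no crossover rate, post-switch effect or OS median for the power claim. The 85% crossover reported in Protocol 1.1.2 is a share of patients randomized to placebo in the earlier regorafenib trial, so it does not bound the share of progressors switching here.

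**OS matters only if PFS and ORR succeed.** True, but that is the situation for which the sequence is written.

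**Conclusion.** Wrong as written. SAP Section 6 is false for the OS primary analysis and for the Cox model form, and it omits the OS interim spending. The defect is an undeclared protocol–SAP conflict on an alpha-controlled endpoint and should be corrected before database lock. Its effect ranges from the HR and CI alone (test of psi = 0, same stratification) to loss of the 5% level if RPSFT were used confirmatorily with an ordinary test on transformed times. The 9–14% for that case is illustrative and depends on the assumptions in Step 2.

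The power point is real but secondary. The 90% holds if the ITT HR, after whatever crossover occurs, is 0.67. If 0.67 is the effect without crossover, power is lower: 83%, 65% or 44% if dilution brings the ITT HR to 0.70, 0.75 or 0.80. Where in that range the trial would fall cannot be read from the documents.

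**What to change.** Before database lock, in the SAP:

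1. **Section 6:** replace the no-change sentence with the actual changes and their reasons, namely the OS primary analysis, the OS interim spending and the Cox model form.
2. **Sections 4.6.1 and 4.6.3.2:** confirm the stratified ITT log-rank test, with the spending already described, as the single confirmatory OS test. RPSFT stays supportive.
3. **Section 7.4:** give the RPSFT HR a confidence interval that carries the uncertainty in psi (test-based or bootstrap), and state that no p-value from transformed times is used for inference.
4. **Section 1.3:** state that the 90% OS power holds only if the ITT HR after crossover is 0.67, and add the power figures by ITT HR from Step 4.

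At the next amendment, bring Protocol 10.5.3.2.2, the Study Summary and Protocol 10.2 into line, including one Cox model form.

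**Cost.** The SAP corrections are wording, with no new data or patients. Aligning the protocol is dearer: under Protocol Section 13 a permanent change is an amendment that needs IRB/IEC approval and regulatory submission, for a study planned at about 90 sites (Protocol 10.2). The stated OS power will also look less favourable if 0.67 was meant as the effect without crossover.

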#### 10.5.3.2.3 Analyses of Health-Related Quality-of-Life

The EORTC-QLQ-C30 questionnaire will be used to collect data on the patient's functioning, disease-related symptoms, and health-related QoL. For all individual scores, eg, physical functioning, pain, role functioning, and appetite loss, etc, mean changes from baseline to Week 12 will be compared between treatment groups by a t-test. Post hoc analyses to explore thresholds for meaningful change using cumulative distribution function to determine clinical benefit will be outlined in the SAP.

#### 10.5.3.2.4 Disease Control Rate

Disease control is defined as rate of CR or PR of any duration, or SD lasting for at least 16 weeks per mRECIST version 1.1 from the beginning of treatment. Disease control rate will be analyzed similarly as the ORR.

